1 OVERVIEW AND INVESTIGATIONAL PLAN

1.1 STUDY DESIGN

This is an open-label, multi-center, non-comparative, Phase 1/2 study to evaluate the safety, preliminary efficacy and PK of isatuximab in combination with REGN2810 (cemiplimab) or isatuximab alone in patients with advanced malignancies.

The study will be conducted in up to 3 parts:

- The Phase 1 part (safety run-in) is to characterize the safety and tolerability of isatuximab in combination with REGN2810 and to confirm the recommended phase 2 dose (RP2D)
- The Phase 2 part (efficacy signal search with Simon's 2-stage design) is to assess the preliminary efficacy of isatuximab in combination with REGN2810 or isatuximab alone
- Cross-over part (a subpart of Cohort A-2) in which patients who progress on isatuximab monotherapy may receive isatuximab plus REGN2810 if they still fulfill the eligibility criteria (except exclusion criteria #3 and #8)

Isatuximab and REGN2810 are defined in this protocol as “study treatments”.

1.1.1 Phase 1 part (safety run-in)

Patients with either metastatic, castration resistant prostate cancer (mCRPC) or non-small cell lung cancer (NSCLC) will be enrolled in the Phase 1 part. There is no minimum patient number requirement for either tumor type.

1.1.1.1 Starting dose and de-escalation design

The starting dose is selected based on past and ongoing clinical trials. Starting dose is 350 mg Q3W for REGN2810 with isatuximab given 10 mg/kg QW for 3 weeks followed by Q3W. Dose de-escalation will be performed if necessary as defined in [Table 1](#) below:

Table 1 - Dose modification for Phase 1

Dose level	Isatuximab	REGN2810
Starting dose	10 mg/kg QW x 3->Q3W	350 mg Q3W
Minus 1 (DL-1)	5 mg/kg QW x 3->Q3W	350 mg Q3W

Abbreviations: DL=dose level; QW=once weekly; Q3W=once every 3 weeks.

At the starting dose, dose limiting toxicity (DLT) will be assessed in the first 6 patients (1 cycle; 21 days):

- If $\leq 1/6$ patient has DLT, the starting dose will be the RP2D
- If $2/6$ patients have DLT, 6 additional patients will be enrolled at starting dose level:
 - If a total of $2/12$ patients treated at starting dose have DLT, starting dose will be the RP2D
 - If a total of $\geq 3/12$ patients have DLT, dose will be de-escalated to dose level minus 1 (DL-1)
- If $\geq 3/6$ patients have DLT, dose will be de-escalated to DL-1

An additional 6 patients may be enrolled at DL-1; if $\leq 1/6$ patient has DLT, DL-1 will be the RP2D. At DL-1, if $\geq 2/6$ patients have DLT, an alternative dose/schedule might be considered from a safety viewpoint by the Sponsor after consulting with the Investigators who recruit patients for the Phase 1 part.

The DLT observation period is 1 cycle (21 days). The duration of the DLT observation period will be longer for patients who delay initiation of Cycle 2 due to treatment-related adverse event (AE) for which the duration must be assessed in order to determine if the event is a DLT. All AEs during treatment, unless due to disease progression or an obviously unrelated cause, will be taken into consideration by the Sponsor and recruiting Investigators for the determination of the maximum tolerated dose (MTD) and RP2D.

Investigational medicinal product (IMP) initiation of patients in the Phase 1 part is to be staggered by ≥ 3 days. The National Cancer Institute (NCI) common terminology criteria for adverse events (CTCAE) version 4.03 will be used to assess the severity of AEs. Causal relationship is to be determined by the Investigator. The DLTs will be confirmed by the Sponsor and recruiting Investigators.

1.1.1.2 Maximum tolerated dose

The MTD is defined as the highest dose level at which no more than 1 out of 6 patients (starting dose or DL-1) or 2 out of 12 patients (starting dose) experience an IMP related DLT. The RP2D is defined as the dose selected for the Phase 2 portion.

1.1.2 Phase 2 part (efficacy signal)

The Phase 2 part may include up to 5 cohorts:

- Cohort A-1: mCRPC, isatuximab and REGN2810 combination therapy
- Cohort A-2: mCRPC, isatuximab monotherapy
- Cohort B: NSCLC, isatuximab and REGN2810 combination therapy
- Possibly Cohort C: mCRPC, isatuximab and REGN2810 combination therapy, or isatuximab monotherapy without initial isatuximab weekly dosing
- Possibly Cohort D: NSCLC, isatuximab and REGN2810 combination therapy without initial isatuximab weekly dosing

Enrollment in Cohort A-2 will start only if the decision to proceed to Phase 2 Stage 2 in Cohort A-1 is made.

The patients treated at the RP2D of isatuximab and REGN2810 in combination during Phase 1 will be included in the efficacy analysis together with patients of the same tumor type in Stage 1 of Phase 2. Based on the number of objective responses (observed up to 6 cycles after the last ongoing patient receives first dose of IMP) and the totality of data observed within a treatment cohort in Phase 2 Stage 1, the Sponsor may decide to advance such a treatment cohort to Phase 2 Stage 2 after consulting with Investigators. After enrollment completion of Phase 2 Stage 1, if efficacy results do not warrant initiation of Stage 2, enrolment will be paused until sufficient results or analyses warrant initiation of Phase 2 Stage 2.

For patients with mCRPC, if it is decided to run Phase 2 Stage 2, an isatuximab monotherapy cohort will be initiated for this population (Cohort A-2); patients with mCRPC will be randomly assigned in a 1:1 randomization ratio to enter Cohort A-1, isatuximab and REGN2810 combination (Phase 2 Stage 2) or Cohort A-2, isatuximab monotherapy (Phase 2 Stage 1). The isatuximab single agent dose and schedule for cohort A-2 is 10 mg/kg QW for 3 weeks followed by Q3W.

Based on the efficacy signal and the totality of data observed within a tumor type at end of Phase 2 Stage 2, the Sponsor may decide to further study isatuximab 10 mg/kg Q3W in combination with REGN2810 or isatuximab 10 mg/kg Q3W as a monotherapy in patients with mCRPC (Cohort C) or isatuximab 10 mg/kg Q3W in combination with REGN2810 in patients with NSCLC (Cohort D), without the isatuximab doses of 10 mg/kg QW for 3 weeks. The schedule without the initial weekly dosing may be more practical for patients and health care providers. Objectives and study design considerations for Cohort C and Cohort D are the same as those for other cohorts in the same tumor type. The Sponsor may decide to test an isatuximab dose of 20 mg/kg in case of inadequate efficacy and PK results.

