Tumor genetic markers (blood) W		Х			X (Cycle 2 and Cycle 3 only)	Х			
Immunophenotyping (blood) X		Х			X (Cycle 2, Cycle 3, then every other cycle)	Х	Х		
Plasma or serum cytokines (blood) y	Х	Х			X (Cycle 2, Cycle 3, then every other cycle)	Х	Х		
Disease Assessment									
- CT/MRI Z	Х				X (repeat every 9 weeks)	Х		Х	
- PSA assessment aa	Х	x k			X (repeat every 9 weeks)	Х		Х	
- Bone scan bb	Х				X (repeat every 9 weeks)	Х		Х	
Isatuximab Administration CC		Х	Χ	Χ	X				
REGN2810 Administration CC		Х			X				
AE/SAE Assessment dd	Х	Continuously throughout study period		iod			, new related AE/SAEs)		
Prior/Concomitant Medication	X (within 28 days prior to first dose)		Continuously throughout study period X (related to AE/SAEs)			AE/SAEs)			
New anticancer therapy						Х	>	1	Х
Survival status								Х	X

- a **Evaluation:** Assessments to be performed prior to study treatment and prior to premedication administration unless otherwise indicated. Inform consent should be signed before any study specific procedures. It can be signed more than 28 days prior to enrollment/randomization. Screening time indicates the time frame in which study procedures used to support eligibility have to be done prior to enrollment/randomization.
- b **Cycle:** A cycle is 21 days. The treatment window is ±1 day for each of the weekly administrations and ±2 day for each of the Q3W administrations. A dose is deemed to have been delayed if the treatment is ≥2 days beyond the theoretical day of treatment for Q3W dose. The window for blood chemistry, hematology, urinalysis, PSA assessment (Cycle 1 Day 1 only), and biomarker blood draw is within 1 day prior to IMP administration (where applicable) for Cycle 1 and beyond.
- c Follow-up: Patients who discontinue the study treatment without PD will be followed every 90 days for disease assessment until confirmation of PD or start of treatment with another anti-cancer therapy, or until study cut-off date, whichever comes first. The further follow-up schedule beyond 90 days after last dose of IMP is according to the disease progression status:
  - Patients who discontinue study treatment due to PD: phone call follow-up will be done every 90 days from the date of last IMP administration until death or study cut-off date.

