- x Immunophenotyping: a sample of peripheral blood will be drawn at Cycle 1 Day 1, Cycle 2 Day 1 and Cycle 3 Day 1 and then on Day 1 prior to IMP administration of each odd cycle starting from Cycle 5 (eg Cycle 5, Cycle 7, Cycle 9, Cycle 11, etc), at the EOT visit, and at follow-up (60 days after last IMP administration).
- y Plasma or serum cytokine concentration: A sample of peripheral blood will be drawn at baseline and Cycle 1 Day 1, Cycle 2 Day 1, Cycle 3 Day 1 and then on Day 1 prior to IMP administration at each odd cycle starting from Cycle 5 (ie, Cycle 5, Cycle 7, Cycle 9, Cycle 11 etc), at the EOT visit and at follow-up (60 days after last IMP administration).
- z Tumor assessment: CT or MRI of the chest, abdomen, pelvis and any other locations with suspicion or evidence of disease involvement is to be performed in all patients at screening (diagnostic quality scans performed as part of routine clinical management within 28 days prior to IMP initiation are acceptable). Repeat every 9 weeks starting at the end of Cycle 3 (63 ±7 days; disease assessment timing should follow calendar days and should not be adjusted for delays in cycle start), whenever disease progression is suspected, at the EOT visit (if not performed in the past 30 days) and during follow-up (if discontinue IMP without PD, repeat every 90 days), using the same method for each assessment. If tumor assessment status is partial or complete response, changes in tumor measurements must be confirmed by repeat assessments that should be performed no less than 4 weeks after the criteria for response are first met. Initial evidence of progression should be confirmed no less than 4 weeks later, see Section 6.7.1. Tumor assessment is not needed for patients who start another anti-cancer treatment regimen. Study sites must retain disease assessment images, as Sponsor may decide to collect these images for possible Independent Central Review in the future.

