### 6.3 PHASE 2 PART (EFFICACY SIGNAL)

The Phase 2 part may include up to 5 cohorts (see design diagram in Section 1.1):

- Cohort A-1: mCRPC, isatuximab and REGN2810 combination therapy.
- Cohort A-2: mCRPC, isatuximab monotherapy.
- Cohort B: NSCLC, isatuximab and REGN2810 combination therapy.

- **Possibly Cohort C**: mCRPC, isatuximab and REGN2810 combination therapy, or isatuximab monotherapy without initial isatuximab weekly dosing.
- **Possibly Cohort D**: NSCLC, isatuximab and REGN2810 combination therapy without initial isatuximab weekly dosing.

A Simon's 2-stage design will be used in each cohort. Enrollment in Cohort A-2 will start only if the decision to proceed to Phase 2 Stage 2 in Cohort A-1 is made.

The patients treated at the RP2D of isatuximab and REGN2810 in combination during Phase 1 will be included in the efficacy analysis together with patients of the same tumor type in Stage 1 of Phase 2. Based on the number of objective responses (observed at least 6 cycles after the last ongoing patient receives first dose of IMP) and the totality of data observed within a treatment cohort in Phase 2 Stage 1, the Sponsor may decide to advance such a treatment cohort to Phase 2 Stage 2 after consulting with Investigators. After enrollment completion of Phase 2 Stage 1, if efficacy results do not warrant initiation of Stage 2, enrolment will be paused until sufficient results or analyses warrant initiation of Phase 2 Stage 2.

For patients with mCRPC, if it is decided to run Phase 2 Stage 2, an isatuximab monotherapy cohort will be initiated for this population (Cohort A-2); patients with mCRPC will be randomly assigned in a 1:1 randomization ratio to enter Cohort A-1, isatuximab and REGN2810 combination (Phase 2 Stage 2) or Cohort A-2, isatuximab monotherapy (Phase 2 Stage 1). The isatuximab single agent dose and schedule for cohort A-2 is 10 mg/kg QW for 3 weeks followed by Q3W.

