#### 9.6 EFFICACY

#### 9.6.1 Primary endpoint

The primary endpoint for the Phase 2 part of the study is RR. The RECIST 1.1 criteria (Appendix B) will be followed for assessment of tumor response in patients with NSCLC (54).

The PCWG3 criteria (Appendix A) will be followed for the assessment of tumor response in patients with mCRPC (48). For patients with mCRPC, response will be defined by radiographic objective response assessed and confirmed by the Investigators and/or a PSA decline of ≥50% from baseline that is subsequently confirmed per PCWG3 criteria (Appendix A). The PSA decline must be confirmed to be sustained by a second PSA value obtained 4 or more weeks later.

The following disease assessment procedures will be performed at screening (for eligibility) and again at Cycle 1 Day 1 (if needed) prior to study treatment administration (baseline for response assessment) and then as detailed below:

- Tumor imaging: performed at screening (diagnostic quality scans performed as part of routine clinical management are acceptable) and then repeated every 9 weeks starting at the end of Cycle 3 (63 ±7 days; disease assessment timing should follow calendar days and should not be adjusted for delays in cycle start), whenever disease progression is suspected, at the EOT visit (if not performed in the past 30 days) and during follow-up (if discontinue IMP without PD), using the same method (CT or MRI) for each assessment. If tumor assessment status is partial or complete response, changes in tumor measurements must be confirmed by repeat assessments that should be performed no less than 4 weeks after the criteria for response are first met.
- **Prostate-specific antigen assessment for patients with mCRPC:** performed at baseline (within 14 days before initiation of IMP). Repeat at Cycle 1 Day 1 and every 9 weeks starting at the end of Cycle 3 (63 ±7 days; disease assessment timing should follow calendar days and should not be adjusted for delays in cycle start), at the EOT visit (if not performed in the past 30 days) and during follow-up (if discontinue IMP without PD). PSA responses are to be confirmed no less than 4 weeks later.

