#### OVERALL RATIONALE FOR THE AMENDMENT

The main reason for this amendment was to modify the inclusion criteria for patients with nonsmall cell lung cancer (NSCLC) by allowing patients with NSCLC with best response as complete response (CR), partial response (PR) or stable disease (SD) at ≥1 radiographic imaging scan who had progressed radiographically to participate. Additional changes for patients with NSCLC include not requiring a tumor biopsy to qualify for enrollment if the procedure could put the patient at excessive risk and minimizing the number of pharmacokinetic (PK) and anti-drug antibody (ADA) samples to be collected. For all patients, premedication requirements were modified to allow patients with no or Grade ≤2 infusion associated reactions to omit premedications at Investigators' discretion. The window for collection of follow-up samples was also extended and text clarified that the follow-up period could extend beyond 6 cycles.

Section # and Name	Description of Change	Brief Rationale
Clinical Trial Summary Section 6.3 Phase 2 part (efficacy Signal)	In Part 2, the observation period after last dose of IMP was changed from up to 6 cycles to at least 6 cycles.	Clarified that due to the time needed to analyze biomarker and PK samples, the totality of data could be generated after the last ongoing patients in individual cohort received 6 cycles.
Clinical Trial Summary Section 1.3 Study flowchart for Phase 1, Phase 2 cohorts A-1, A-2, B and cross-over part	I 03: For NSCLC patients, the mandatory tumor biopsy requirement was modified to allow a patient to enter the study without a tumor biopsy at baseline if, in the written opinion of the investigator, performing a biopsy would put the wellbeing of the patient at an excessive risk due to the location of the lesion. Written agreement from the	To decrease risk for patients with NSCLC whose lesion is located in a site where performing a biopsy would but the wellbeing of the patient at an excessive risk.
Section 1.4 Study Flowchart for cohort C and cohort D	Sponsor was required.	
Section 7.2 Inclusion criteria		
Section 9.3 Biomarkers		
Clinical Trial Summary Section 7.2 Inclusion criteria	I 12 Added that patients with NSCLC could enter the study with inoperable recurrent NSCLC rather than only Stage IIIB/IV NSCLC.	To clarify that patients with inoperable recurrent NSCLC could be enrolled.

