3 INTERIM ANALYSIS (IA)

An IA will be performed for each cohort after the first 23 patients for mCRPC cohorts or the first 20 patients for NSCLC cohorts in the Phase 2 part have completed 6 cycles. The interim analysis may be conducted earlier if the required number of responders proceeding to Phase 2 Stage 2 is achieved.

The analysis will include the following parameters/analyses (defined in [Section 2.1](#)): response rate, demographics and baseline characteristics, prior or concomitant medication, AEs (TEAE, death, SAE, TEAE leading to discontinuation, IAR, AESI), and laboratory variables (abnormality of hematological and chemistry test). If needed, more data will be analyzed to inform the futility decision including additional efficacy, PK, and biomarker.

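### SAP 1.1.2 makes 6 cycles a ceiling for Stage 1 responses where the protocol makes it a floor, so a week-18 response in the last-enrolled patients may be unconfirmed at the look

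*SAP*

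**What the plan says.** The two documents bound the Stage 1 response window in opposite directions.

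- SAP 1.1.2 uses objective responses "observed up to 6 cycles after the last ongoing patient receives first dose of IMP".
- Protocol 6.3, and the same text in the Clinical Trial Summary, uses those "observed at least 6 cycles after the last ongoing patient receives first dose of IMP".
- The amendment history (protocol Appendix J, Amended Protocol 04 of 21 November 2018) records that the observation period "was changed from up to 6 cycles to at least 6 cycles". The SAP therefore carries the replaced wording. SAP 1.5 lists no modification to the protocol's statistical section.

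The interim trigger is the same in SAP 3 and protocol 13.5: the look follows once the first 23 mCRPC or first 20 NSCLC patients "in the Phase 2 part have completed 6 cycles". It may come earlier if the required number of responders has been reached.

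On timing, the protocol 1.3 flowchart footnotes state that "A cycle is 21 days" and, for imaging, "Repeat every 9 weeks starting at the end of Cycle 3 (63 ±7 days", on calendar days. PSA follows the same 9-week schedule. Protocol 9.6.1 requires confirmation of a radiographic response by "repeat assessments that should be performed no less than 4 weeks after the criteria for response are first met", with the same 4-week minimum for PSA. SAP 2.1.3.1 counts only confirmed responses.

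**The concern.** A response first seen at the second scheduled assessment cannot be confirmed on the same day. If the Stage 1 count closes at 6 cycles after the last patient's first dose, such a response in the most recently enrolled patients is left out even if it is later confirmed. Protocol Appendix A (Table 11) warns that a PSA benefit may take 12 weeks or more to appear. With PSA taken every 9 weeks, the first scheduled value after week 12 is the one at week 18, so late first responses are a real possibility in mCRPC.

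The Stage 1 thresholds (3 of 23, 2 of 20) and the stated 90% power assume that every confirmed response among Stage 1 patients is available to the decision. Missing some of them makes it more likely that an active cohort fails the threshold. For Cohort A-1 this reaches further, because Cohort A-2 opens only if A-1 proceeds.

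The interim trigger does not repair this. It does not require a wait for confirmation, and a patient who stops early never completes 6 cycles, so read literally the trigger may never be met.

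**Working it through.** **Timing.** Six cycles = 6 × 21 = 126 days = week 18, with a scan window of days 119 to 133. Earliest confirmation of a response first seen on day 126 is 126 + 28 = day 154 (week 22), or 119 + 28 = day 147 (week 21) for an early scan.

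The cut is anchored to the last patient's first dose. A patient who started *d* days earlier has 126 + *d* days of follow-up at the cut. Confirmation of a day-126 response fits if 126 + *d* ≥ 154, that is *d* ≥ 28. With the ±7-day scan window this becomes 21 to 35 days. Only patients who started within about 3 to 5 weeks of the last one are exposed.

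**The plan's own figures.** From protocol Table 8: mCRPC 10% vs 26%, continue at ≥3/23, reject at ≥9/49; NSCLC 5% vs 22%, continue at ≥2/20, reject at ≥5/36. With X₁ ~ Bin(n₁, p) and Y ~ Bin(N − n₁, p),

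Power = Σ over x ≥ r₁ of P(X₁ = x) · P(Y ≥ r − x).

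| | alpha | power | P(fail Stage 1) at H₁ |
|---|---|---|---|
| mCRPC | 0.0479 | 0.9015 | 0.0396 |
| NSCLC | 0.0294 | 0.9018 | 0.0461 |

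The stated 90% power at 5% one-sided alpha is reproduced.

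**Effect of the cut.** Let *k* be the number of Stage 1 patients who started within about 4 weeks of the last one, and *f* the share of eventual confirmed responses first seen at week 18. Neither is in the documents; both are assumptions. At the look,

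- early starters: Bin(n₁ − k, p);
- late starters with a countable response: Bin(k, p(1 − f));
- pending responses among the remaining late starters: each with probability pf / (1 − p(1 − f)).

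The cohort continues if the countable responses reach r₁. Pending responses count at the final analysis only if it continues. The Stage 1 rule is treated as binding, which is the worst case.

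| k, f | mCRPC power | NSCLC power |
|---|---|---|
| none lost | 0.9015 | 0.9018 |
| 1, 10% | 0.9008 | 0.9010 |
| 3, 33% | 0.8939 | 0.8935 |
| 6, 10% | 0.8971 | 0.8969 |
| 6, 33% | 0.8840 | 0.8828 |
| 10, 50% | 0.8364 | 0.8325 |

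For k = 1 to 6 and f = 10 to 33%, the loss runs from 0.9015 − 0.9008 = 0.0007 (about 0.1 point) to 0.9018 − 0.8828 = 0.0190 (1.9 points). At k = 10 and f = 50% it is 0.9015 − 0.8364 = 6.5 points for mCRPC and 0.9018 − 0.8325 = 6.9 points for NSCLC. If the look waits for the week-18 confirmations, the planned figures return.

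Missed responses can only add stops, so alpha does not rise above the planned values.

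**The case against.** The strongest reply is that the Stage 1 rule is not a mechanical count. SAP 1.1.2 rests the decision on responses together with the totality of data, SAP 3 allows further efficacy data to be brought into the futility decision, and without a go enrolment is paused rather than closed. A sponsor who knew of a pending week-18 response could wait. This stands: the consequence is a possible wrong pause, and the power figures above are a worst case. It does not settle which responses are to be counted.

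Second, SAP 1.1.2 speaks of responses observed, not confirmed, by 6 cycles. Elsewhere (SAP 2.1.3.2) a response is dated to its first occurrence, subject to later confirmation. A first response at week 18 with later confirmation could then be counted. That reading is tenable, but the SAP does not state it, and it would still need the decision to wait.

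Third, the protocol wording alone does not force the wait. It permits a later look, and the amendment's stated reason was processing time for biomarker and PK samples. That is correct, so aligning the SAP is necessary but not sufficient.

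Three stronger readings are tempting and not supported:

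- A reader might apply the loss to every Stage 1 patient. That gives 0.842 (mCRPC) and 0.851 (NSCLC) at 20%, and 0.756 and 0.784 at 33%. But the cut follows the last patient, so earlier starters have longer follow-up. With one third of responses late, losing 20% across 23 patients needs 0.20 × 23 ÷ (1/3) ≈ 14 late starters. Phase 1 patients treated at the RP2D also count in Stage 1, and they started earlier.
- A reader might infer that the look selects patients who completed 6 cycles. SAP 2.3.1 and 2.4.5 make all-treated the primary efficacy population, which largely answers this. The trigger wording is still loose.
- A reader might infer harm to the final inference. The response-rate cut-off is 6 months after the last patient's first treatment (SAP 2.4.5), later than week 22.

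**Conclusion.** The SAP and the current protocol conflict on the Stage 1 response window. Read strictly, the SAP version excludes a first response at week 18 in patients who started within about 4 weeks of the last Stage 1 patient. The shared interim trigger does not require the wait either, and early discontinuers never meet it.

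The effect is on the go/no-go decision only: a possible wrong pause of an active cohort, and for A-1 a delay to A-2. Under a binding count, the loss is under 2 points of power for 1 to 6 late starters with 10 to 33% late responses, and about 7 points in the more extreme case of 10 and 50%. These sizes rest on assumed accrual and response timing, so the direction is firm and the amount is not. The defect is worth correcting because the rule is wrong as written and cheap to put right, not because a large loss of power has been shown.

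**What to change.** 1. In SAP 1.1.2, adopt the protocol's wording, "observed at least 6 cycles after the last ongoing patient receives first dose of IMP".
2. In SAP 3 and protocol 13.5, state that the look counts all treated Stage 1 patients, whether or not they are still on treatment.
3. In the same two sections, state that a no-go is not declared until any response first seen at the week-18 assessment of the last Stage 1 patient has had its confirmation assessment at least 4 weeks later. That falls about 22 weeks after that patient's first dose (126 + 28 = 154 days), or up to 24 weeks if 7 days are allowed on each visit (126 + 7 + 28 + 7 = 168 days). The protocol gives no upper window for the confirmation visit, so the exact margin is a choice.
4. Keep the early go: a cohort may proceed as soon as the required number of confirmed responses is reached.

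The cost is a SAP wording change and a short protocol clarification. A no-go decision comes about 4 to 6 weeks later (week 22 to 24 instead of week 18); a go is not delayed.
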